## Appendices

### 18.1 Protocol Deviations Identified by Programming and Clinically Important Events

Inclusion and exclusion criteria are referenced according to Protocol MS201408-0005 version 2.0 dated 08-Sep-2017.

	Description	Code	Clinically Important?	Protocol Section	Proposed Check / Comment
Inclusion / Exclusion Criteria					
Violated eligibility criteria	Any "no" response to inclusion criteria and/or any "yes" response to exclusion criteria, and subject was subsequently entered into the study	INCEXC01			Violations should be documented on the Study Entry CRF page, which is mapped to the IE domain in SDTM
Informed Consent / Subject Information					
Late ICF signature	ICF was signed after study procedure was done	INFCON03			Check that no dates are prior to ICF date
Investigational Product					
Overdose	Subject received $\geq 110\%$ of the calculated dose for that particular administration	INVPR06			Flag if relative dose intensity $\geq 1.10$
Pharmacokinetics-Related					
Vomiting	Vomiting immediately following oral dosing that can affect a PK result	PK001			Manual check by PK scientist
Sample processing errors	Errors that lead to inaccurate bioanalytical results	PK002			Manual check by PK scientist
Inaccurate dosing, dose reductions, dose errors, missed doses	Inaccurate dosing, dose reductions, dose errors, or missed doses that can affect the PK results on one or more PK days	PK003			Manual check by PK scientist

## **List of Abbreviations and Definition of Terms**

ADA	Anti-drug antibody
AE(s)	Adverse event(s)
AESI(s)	Adverse event(s) of special interest
AUC	Area under the drug concentration-time curve
AUC 0-8	Area under the drug concentration-time curve from 0 to 8 h postdosing
BID	Twice daily
BOR	Best overall response
C max	Maximum plasma concentration observed postdose
C min	Minimum observed postdose (trough) plasma concentration
CTCAE 4.03	Common Terminology Criteria for Adverse Events Version 4.03
cQTc	Concentration-QTc
DCR	Disease control rate
DLT	Dose-limiting toxicities
DOOR	Duration of response
ECG	Electrocardiogram
ECOG PS	Eastern Cooperative Oncology Group Performance Status
eCRF	Electronic case report form
eDISH	Evaluation of drug-induced serious hepatotoxicity
iAP	Integrated analysis plan
IC 50	Half maximal effective concentration
IDO	Indoleamine-2, 3-dioxygenase
CCI	■■■■■
MedDRA	Medical Dictionary for Regulatory Activities
MTD	Maximum tolerated dose
OBD	Optimal biological dose
PD	Pharmacodynamics
PFS	Progression-free survival
PK	Pharmacokinetic(s)
PT	Preferred Term
QD	Once daily

QTc	Corrected QT interval
RP2D	Recommended Phase II dose
SAE	Serious adverse event
SMC	Safety Monitoring Committee
SOC	System Organ Class
TDO	Tryptophan-2, 3-dioxygenase
TEAE	Treatment emergent adverse event
CCI	
TLFs	Tables, Listings, and Figures
t max	Time to reach maximum concentration
TRAE	Treatment related adverse event
CCI	
ULN	Upper limit of normal

## 4 Modification History

Unique Identifier for iAP Version	Date of iAP Version	Author	Changes from the Previous Version
1.0	30 January 2018	PPD [REDACTED]	N/A – first version

## 5 Purpose of the integrated Analysis Plan

The purpose of this integrated Analysis Plan (iAP) is to document technical and detailed specifications for the analyses performed for the Safety Monitoring Committee (SMC) reviews of data collected for protocol MS201408-0005. Results of the analyses described in this iAP will be used (amongst other data) by the SMC to decide upon dose and size of future cohorts. This iAP will specify the Bayesian two-parameter logistic regression model used to make a recommendation to the SMC for dose escalation. Additionally, this iAP will describe preliminary PK analyses for M4112, as well as Tables, Listings, and Figures (TLFs) summarizing safety data. The latter will only be applicable if an SMC meeting is adjourned and at data of at least 6 treated subjects in the respective treatment arm. The TLFs (except for the overall listing of AEs, the PK analyses and CCI [REDACTED] analyses) will be produced on the SDTM data available at cut-off (usually from previous cut-off) except a listing of all AE and a listing of all AE >= grade 3, that will be produced in JReview along with the patient profiles. CCI [REDACTED]

The iAP is based upon Section 8 (Statistics) of the trial protocol and protocol amendments and is prepared in compliance with ICH E9.

## 6 Summary of Clinical Trial Features

### Objectives:

#### Primary Objectives

##### Part IA (Dose Escalation – M4112 as Single Agent)

- To determine safety and tolerability or, if observed, the maximum tolerated dose (MTD), and to define the recommended Phase II dose (RP2D) of M4112 as single agent in subjects with solid tumors.

CCI [REDACTED]

CCI [REDACTED]

- CCI [REDACTED]

#### Secondary Objectives

##### Part IA (Dose Escalation – M4112 as Single Agent)

- To characterize the PK parameters of M4112 as single agent
- To assess QT prolongation potential by central tendency, outlier analysis and the slope of exposure-QTc analysis
- To evaluate preliminary clinical activity parameters using RECIST 1.1.

CCI [REDACTED]

CCI [REDACTED]

CCI [REDACTED]

#### Methodology:

This study is a Phase I, open-label study designed to determine the safety, tolerability, PK, PD, and preliminary antitumor activity of M4112 as single agent (Part IA only) CCI [REDACTED]

[REDACTED] The target population for Part I (Dose Escalation) comprises of subjects with advanced or metastatic solid malignancies for whom no effective standard therapy exists or has failed or subjects who are intolerant to established therapy known to provide clinical benefit for their condition.

##### Part IA CCI Dose Escalation

A broad dose range in monotherapy will be investigated to determine the safety profile, tolerability, PK, and PD markers and to explore signs of antitumor activity in subjects with advanced solid tumors.

Subjects will receive M4112 at the starting dose of 100 mg BID (100 mg BID which equals to 200 mg total daily dose) at least 1 h prior to a meal and at least 2 h after a meal. Cohorts will consist of 3 subjects each, if not decided differently by the SMC. The first subject of each dose level will be observed for at least 5 days before the second subject can be treated. Subsequent subjects may receive first dosing at no less than 48 h intervals between subjects for the first 2 cohorts of mono and combination therapy. If the safety profile is acceptable and agreed by the SMC, the 48 h observation after Subject 2 may be removed). The safety and tolerability data and available PK and PD data (as minimum Day 1 and Day 15 PK and PD data from

previous cohort and all available PK and PD data from the current cohort) will be reviewed by the SMC at the end of each cohort. In cases where enrollment of last subject in a dosing cohort is delayed, the SMC may decide (based on available data) upon enrollment and dose for the next dosing cohort before all subjects in a cohort have completed Cycle 1. The SMC will be assisted in their dosing and regimen (administration schedule) decisions by PK, PD, and a Bayesian 2-parameter logistic regression model modeling dose-limiting toxicity (DLT) rate with overdose control. The model incorporates nonclinical toxicity data in the prior and DLTs observed until the SMC to provide a recommended dose for the next cohort. During the dose escalation part of the study, the SMC will advise, primarily based on safety (DLTs) and additional data relevant for the treatment, on dose escalation, dose de-escalation, dose level expansion or regimen change, or it may recommend suspension of enrollment, with the final decision being a Sponsor decision. The SMC may also recommend a cohort size different from 3 subjects as the Bayesian design allows dose recommendation based on less or more than 3 subjects.

Prespecified ascending doses of 100, 200, 400, 600, 800, and 900 mg BID (means respectively, 100 mg BID for 200 mg total daily dose, 200 mg BID for 400 mg total daily dose, 400 mg BID for 800 mg total daily dose, 600 mg BID for 1,200 mg total daily dose, 800 mg BID for 1,600 mg total daily dose, 900 mg BID for 1,800 mg total daily dose) as single agent in 28-day cycles are foreseen. Dose escalation decisions will be driven primarily by DLT, safety, and tolerability. **CCI**

A BID dosing regimen will be followed, based on PK modelling, to achieve the target  $C_{min}$  over the dosing interval at a lower total daily dose and thereby reducing  $C_{max}$  and AUC over the day to potentially improve safety and tolerability when compared to once daily (QD) dosing. Based on PK data from subjects, the SMC will evaluate whether this regimen can be sustained or needs to be changed.

In principle, dose escalation of single agent M4112 (Part IA) will proceed according to the recommendation of the SMC to at least the upper end of the above given dose range, unless the MTD has been reached or there is excess of PK nonlinearity, or the SMC recommends to end dose escalation following review of safety, tolerability, PK and PD results. Depending on the observed toxicity profile and available PK and PD, a dose regimen different to or dose(s) higher/lower than the prespecified doses may be tested.

The following criteria will be applied to define the RP2D of M4112 as single agent:

- CCI [REDACTED]

- CCI [REDACTED]

This dose level will then be studied in  $\leq 6$  evaluable subjects to establish safety, tolerability, PK, and PD and will be defined as the RP2D of M4112 as single agent.

CCI [REDACTED]

- CCI [REDACTED]

The starting dose of M4112 CCI [REDACTED] will be dependent on the observed safety, tolerability, and PK/PD profile during dose escalation in the single agent cohort (Part IA) and will lag at least 1 dose level behind the last completed safe dose level of M4112 as single agent, which was confirmed as safe by the SMC. CCI [REDACTED]

Separate Bayesian logistic regression models will be used for guidance of dose escalation for each of the combinations.

Dose escalation will proceed until the OBD of M4112 CCI [REDACTED] is reached or dose escalation ends due to occurrence of DLTs establishing MTD or the SMC recommends to end dose escalation following review of safety, tolerability, PK and PD results whatever occurs first. CCI [REDACTED]

CCI [REDACTED]

- CCI [REDACTED]
- CCI [REDACTED]

Once safety and PD effects are confirmed in  $\leq$  6 additional subjects, these dose levels will be used as the RP2D of the respective combination therapies.

#### DLT Definition

DLTs will be used to determine dose escalation, dose de-escalation, and the MTD (if reached), using the National Cancer Institute (NCI) Common Terminology Criteria for Adverse Events Version 4.03 (CTCAE 4.03). DLTs are defined in the clinical study protocol.

CCI [REDACTED]

Subjects with nausea and vomiting will maintain normal schedule without re-dosing.

The MTD is defined by the SMC. An MTD is suggested from the Bayesian logistic regression model with target toxicity of 30%.

Subjects who tolerate M4112 and their combination partner without significant clinically relevant toxicities will continue to receive their assigned dose until discontinuation criteria are met, withdrawal of consent or the study ends, whatever occurs first.

#### **Follow-up Period:**

The Safety Follow-up Visit is scheduled  $30 \pm 3$  days CCI [REDACTED]

after the last dose of M4112 CCI [REDACTED]

or until resolution of AEs to Grade 1, before start of any new anticancer therapy, whatever comes first.

Subjects who discontinue treatment must be followed on study until resolution of toxicity or until confirmed disease progression.

#### **Planned number of subjects:**

**Part I (A CCI Dose Escalation):** Monotherapy escalation A: Approximately 24 subjects, CCI [REDACTED]

**Primary endpoints:**

**Part IA (Dose Escalation – M4112 as Single Agent)**

- Occurrence of DLTs in subjects receiving M4112 as single agent during the first 4 weeks (Day 1 to Day 28 of Cycle 1) of treatment
- Occurrence of treatment-emergent adverse events (TEAEs) and TRAEs according to NCI-CTCAE 4.03 (including deaths) in subjects receiving M4112 as single agent from start of treatment up to the last Safety Follow-up Visit
- Treatment-emergent changes from baseline in clinical laboratory measures, vital signs, Eastern Cooperative Oncology Group Performance Status (ECOG PS), and physical examination findings in subjects receiving M4112 as single agent up to the last Safety Follow-up Visit.

**CCI**

- CCI
- CCI
- CCI
- CCI

**CCI**

- CCI
- CCI
- CCI
- CCI

**Secondary endpoints:**

**Part IA (Dose Escalation – M4112 as Single Agent)**

- Plasma PK parameters for M4112: AUC0-8, Cmax, tmax, AUC0-8/dose, Cmax/dose, (Days 1 and 15), Racc(AUC0-8) and Racc(Cmax) (Day 15), Cmin, and Cmin/dose (Days 8 and 15 of Cycle 1 and Day 1 of Cycle 2)
- Slope of concentration-QTc (cQTc) regression based on time-matched electrocardiogram (ECG) readings (3 or more replicates) and PK samples during Cycle 1 at Day 1 and Day 15, central tendency and outlier analyses for absolute QTcF, and delta QTc
- BOR, DOR, DCR, time to tumor response, and PFS using RECIST 1.1, up to confirmed tumor progression.

**Concentration-QTc and safety ECG:**

Time-matched ECG readings (3 or more replicates) will be collected at -45, -30, and -15 min predose and at 0.5, 1, 2, 3, 4, 6, and 8 h postdose, just prior to PK sample collections during Cycle 1 at Day 1 and Day 15 during Part IA (M4112 monotherapy).

CCI

- **Pharmacokinetics:**

- Pharmacokinetic parameters for M4112 will be based on plasma concentrations collected predose and at 0.5, 1, 2, 3, 4, 6 and 8 h postdosing on Days 1 and 15 of Cycle 1. Predose concentrations on Day 8, Cycle 1 and predose and 2 h postdose on Day 1, Cycle 2 will be assessed.

CCI

- CCI

#### Safety assessments:

The safety profile of M4112 will be assessed through the recording, reporting and analysis of baseline medical conditions, adverse events (AEs), adverse events of special interest (AESIs), DLTs in Cycle 1 and any treatment-emergent immune-related AE observed in subsequent cycle (Cycle 2) that in the opinion of the SMC needs to be taken into account for safety and proposal of dose escalation, physical examination findings including vital signs, laboratory tests (chemistry, hematology, and coagulation), ECOG PS, and a 12-lead ECG in triplicate from the date of signature of first informed consent until the either until the  $30 \pm 3$  days Safety Follow-up Visit, CCI

or before the start of any anticancer therapy, whatever comes first.

## 7 Sample Size/Randomization

As inherent in dose escalation studies, the sample size cannot be prespecified. The planned size of each dosing cohort is 3 subjects; however, based on the results of a Bayesian two-parameter logistic model, the SMC may elect to change the size of future cohorts.

## 8 Overview of Planned Analyses

The following analyses requiring an SAP/iAP are planned for this trial:

- SMC analyses (this iAP)
- End of monotherapy dose escalation analysis (separate iAP)
- Primary analysis of escalation part of the trial (separate iAP)

Patient Profiles based on the raw data will also be produced for SMCs, and no separate iAP is needed for this deliverable.

**Cut-off date:**

SMCs are usually planned after the last subject of each cohort has finished the DLT assessment period of 28 days or dropped out of the study. In cases where enrollment of the last subject in a dosing cohort is delayed, the SMC may decide (based on available data) upon enrollment and dose for the next dosing cohort *before* all subjects in a cohort have completed the dosing cycle and thus set an earlier data cut-off, except the first SMC which needs all three subjects have finished the DLT period. For each SMC, a two-parameter logistic Bayesian model will be updated with the observed safety data based on observed DLTs to help the SMC in its dosing decision.

When monotherapy and combination therapy cohorts are open at the same time, efforts will be made to have a joint SMC with a data cut-off at the end of the DLT period for the last subject to be included in the joint SMC.

**8.1 Sequence of Analysis**

Summary TLFs based upon cumulative data within each treatment arm will be created upon availability of data of  $\geq 6$  treated subjects in the respective treatment arm. Analyses and decisions will be made separately for each treatment arm.

**9 Changes to the Planned Analyses in the Clinical Trial Protocol**

There are no changes to the planned analyses.

**10 Analysis Sets**

Analysis sets relevant to SMCs are defined in Table 1.

**Table 1** Analysis Sets

Population	Description
Screening	All participants who sign informed consent.
Dose Escalation	All subjects treated in dose escalation cohorts who do not miss > 5 planned total daily doses of M4112 CCI in the first cycle (first 28 days) of the dose escalation part for other than DLT. The latter only applies to subjects in the combination dose escalation.
Safety	The Safety Analysis Set will include all subjects who receive at least 1 dose of study treatment. In case of combination treatment, study treatment includes also the combination agents.
M4112 Pharmacokinetic	All subjects from the Safety Analysis Set without major protocol deviations/violations or events that would affect PK. Subjects in the PK Analysis Set must have received at least 1 dose of M4112 and must have sufficient M4112 plasma concentration data to enable the calculation of at least 1 PK parameter. Sufficient concentration data is defined as at least 3 valid, postdose concentration points in the PK profile to obtain any PK parameter.
Pharmacodynamics	All subjects who received at least 1 dose of M4112 and provide the predose and at least 1 postdose sample for PD assessment.

ADA = anti-drug antibody; cQTc = concentration-corrected QT interval (QTc); DLT = dose-limiting toxicities; ECG = electrocardiogram; PD = pharmacodynamics; PK = pharmacokinetic.

## 11 General Specifications for Statistical Analyses

All analyses will be separate for each treatment arm (M4112 monotherapy, **CCI** **CCI** **CCI** and so will decisions by the SMC.

### Significance level:

There will be no statistical tests performed in these SMC analyses. If confidence or credibility intervals are mentioned, the level will be 95% unless otherwise specified.

### Presentation of continuous and qualitative variables:

Continuous variables will be summarized using descriptive statistics, i.e.

- number of subjects (N), number of subjects with non-missing values
- mean, standard deviation
- median, 25th Percentile - 75th Percentile (Q1-Q3)
- minimum, maximum

If there are fewer than 5 observations summarized, only the number of subjects (N), number of subjects with non-missing values, the mean, and the values themselves will be given.

Qualitative variables will be summarized by counts and percentages.

Unless otherwise stated the calculation of proportions will be based on the number of subjects in the analysis set of interest. Therefore, counts of missing observations will be included in the denominator and presented as a separate category.

**Definition of baseline:**

In general the last non-missing measurement prior to the first study drug administration will be used as the baseline measurement.

**Definition of duration:**

If not otherwise specified, duration will be calculated by the difference of start and stop date + 1 (e.g. survival time (days) = date of death – date of randomization + 1).

The time since an event (e.g. time since first diagnosis) will be calculated as reference date minus date of event.

**Conversion factors:**

The following conversion factors will be used to convert days into months or years: 1 month = 30.4375 days, 1 year = 365.25 days.

**Handling of missing data:**

Unless otherwise specified (Section 13, 15, 16 and 17), missing data will not be replaced.

In all listings, imputed information will be flagged.

Missing statistics, e.g. when they cannot be calculated, should be presented as “nd”.

Where tables are presented over different time points, the total of missing and non-missing observations at each time-point should reflect the population still in the trial at that time. This does not apply when imputations are made beyond trial withdrawal. For example, if a subject is still in the trial at the time-point but with missing data, they should be counted in the number of missing observations.

Treatment day is defined relative to the date of first study drug administration. Treatment Day 1 is treatment start date of first administration of any of the following study drugs (M4112, CCI [REDACTED], CCI [REDACTED]; the day before is defined as Treatment Day -1 (no Treatment Day 0 is defined).

All analyses (except calculations of posterior distributions, recommended next dose and associated outputs) will be performed using SAS® Software version 9.2 or higher. For the outputs of the Bayesian two-parameter logistic model updates, East® 6.0 or R (version 3.1.2 or higher [Core Team, 2014]) and the R package bcrm [Sweeting, 2013] or crmpack will be used.

## 12 Trial Subjects

Only displayed in Patient Profiles.

## **13 Demographics and Other Baseline Characteristics**

Only displayed in Patient Profiles.

## **14 Previous or Concomitant Medications/Procedures**

Only displayed in Patient Profiles.

## **15 Treatment Compliance and Exposure**

Only displayed in Patient Profiles.

## **16 Endpoint Evaluation**

### **16.1 Primary Endpoint Analyses**

The primary objective of the SMC meetings is to regularly monitor the overall safety of the subjects enrolled in the trial. An important part of that is reviewing DLTs. The primary analysis of DLTs is performed using a Bayesian two-parameter logistic modeling approach to model the relation of dose to the occurrence of DLTs. The results from updating this model will assist the SMC in their dosing decisions.

The SMC will receive patient profiles containing:

- Subject disposition (still in trial, or withdrawn with reason for withdrawal)
- Demographics and baseline characteristics (e.g., cancer diagnosis, staging)
- Medical history
- History of disease under study
- Previous and concomitant medications
- Prior anti-cancer drug therapies
- Prior anti-cancer radiotherapy
- Prior anti-cancer surgeries
- Concomitant procedures
- Study drug administration, dose completion, and dose adjustment
- All serious and non-serious AEs, including but not limited to:
  - DLTs
  - AESIs
  - AEs leading to dose reduction or temporary discontinuation
  - AEs leading to permanent treatment discontinuation

- AEs leading to death
- Laboratory data (hematology, coagulation, biochemistry, urinalysis)
- ECG results, including change from baseline in QTc interval
- Vital signs

Patient profiles will be provided for the current cohorts under review and updated patient profiles will be provided for the previous cohorts (i.e. the cohorts of the last previous SMC in same study part).

In addition, a DLT profile plot of all subjects in the SAF Analysis Set will be produced. This will show an open square for all subjects who did not have a DLT during Cycle 1, a closed square for those who experienced a DLT during Cycle 1, and an open circle for those who were excluded from the DE Analysis Set. This plot will have Cohort Number on the x-axis and dose level (mg) on the y-axis.

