- g On Day 1 and Day 15 of every cycle, vital signs (blood pressure, pulse, respiratory rate, temperature) will be assessed predose (within 15 min of oral dosing after the subject has rested in the semi-recumbent position for 3 to 5 min), and then every 15 min from dosing of M4112 for an additional 2 h. Observation can be extended per investigator's discretion. Height and weight at Screening only.
- h For ECG time points of safety monitoring: Standard triplicate (within 2 min) digital 12-lead ECG will be obtained after the subject has been rested in semi-recumbent position for at least 5 min at Screening, predose and 2, 3, 4 and 8 h postdose on Days 1 and 15 of Cycle 1, predose on Day 8 of Cycle 1, and on Day 1 Cycle 2 (and + 2 h postdose), Day 1 Cycle 4, Day 1 Cycle 6 and then every second cycle thereafter at predose and at least 60 min postdose on these visits. ECGs will be also performed during the End of Treatment and Safety Follow-up Visit (30  $\pm$  3 days). Triplicate ECGs will be read locally. The calculated QTc average of the three 12-lead ECGs must be  $\leq$  450 ms for continued eligibility. Subjects, in which the calculated QTc average increases to  $>$  500 ms or  $>$  60 ms change over baseline during treatment with M4112, have to interrupt study treatment until further clinical evaluation of QT prolongation. During single agent dose escalation (Part IA), replicate digital 12-lead ECGs within 2 min after a minimum of 5 min rest in semi-recumbent position will also be collected on Days 1 and 15 of Cycle 1 for concentration-QTc analysis, for time points, see Table 4. For Part 1A only, replicate ECGs (Holter) will also be collected on Days 1 and 15 of Cycle 1 for exposure-QTc analysis.
- i Hematology includes complete blood count with differential and platelet counts. Blood samples for hematology will be obtained prior to administration of study drug (see Table 10).
- j Coagulation with aPTT and prothrombin time. Blood samples will be collected prior to administration of study drug (see Table 10).

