## 2.1 Safety Monitoring Committee

A Safety Monitoring Committee (SMC) will review the safety data on a regular basis. The SMC consists of members of the Sponsor (Drug Safety Product Leader, Medical Responsible, Clinical Pharmacologist and Biostatistician), the CRO (Medical Responsible) and the Coordinating Investigator. Ad hoc members may be invited as needed. During the dose-escalation part of the study, the SMC will evaluate the safety, tolerability, pharmacokinetics (PK) and available CCI

Based primarily on dose-limiting toxicities (DLTs), the SMC will advise on dose escalation, dose de-escalation, dose expansion, change in administration schedule/regimen (change for example from twice daily [BID] to once daily [QD]), or recommend suspension of enrollment, with the final adjudication being a Sponsor decision. The SMC will recommend the starting dose for M4112 CCI based on the observed safety, tolerability, available PK and PD markers of M4112 as single agent CCI. The SMC will decide, by consensus, on continuation of the study, or recommend modification or suspension of the study, with the final adjudication being a Sponsor decision. During the course of the study, the SMC may modify the frequency of its meetings as deemed appropriate. In cases where enrollment of the last subject in a dosing cohort was delayed, the SMC may decide (based on available data) upon enrollment and dose for the next dosing cohort before all subjects in a cohort have completed Cycle 1. Subjects will be assigned sequentially to cohorts of either M4112 as a single agent, CCI

[figure not shown]
The specific working procedures will be described in an SMC charter, which will be established prior to the start of recruitment.

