### **Abnormal Laboratory Findings and Other Abnormal Investigational Findings**

Abnormal laboratory findings and other abnormal investigational findings (for example, on an ECG trace) should not be reported as AEs unless they are associated with clinical signs and symptoms, lead to treatment discontinuation or are considered otherwise medically important by the Investigator. If a laboratory abnormality fulfills these criteria, the identified medical condition (for example, anemia, increased ALT) must be reported as the AE rather than the abnormal value itself.

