## **17.4 Vital Signs**

Vital signs will only be presented in the Patient Profiles.

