## **17.5 Other Safety or Tolerability Evaluations**

ECG results will only be presented in the Patient Profiles.

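### After the SMC meeting that follows its own review, a cohort's QTc, vital-sign and exposure values appear in no planned SMC output

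*SAP*

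**What the plan says.** All section numbers for the SMC plan refer to SAP Appendix 18.2, dated January 2018.

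- **Profile coverage.** Section 16.1 provides profiles for the current cohorts, and "updated patient profiles will be provided for the previous cohorts (i.e. the cohorts of the last previous SMC in same study part"). The profiles contain "ECG results, including change from baseline in QTc interval", along with vital signs, laboratory data and dosing records.
- **Where the values are shown.** Section 17.5: "ECG results will only be presented in the Patient Profiles". Section 17.4: "Vital signs will only be presented in the Patient Profiles". Section 15, on compliance and exposure: "Only displayed in Patient Profiles".
- **Cumulative outputs.** Section 8.1 makes the summary outputs cumulative within an arm once 6 subjects are treated. Those named in sections 17.1 to 17.3 are adverse event tables and listings and a plot of peak ALT against peak bilirubin.
- **Data collection.** After Cycle 2, safety ECGs are due on "Day 1 Cycle 4, Day 1 Cycle 6 and then every second cycle thereafter" (protocol Table 1, footnote h). Footnote g asks for vital signs on Days 1 and 15 of every cycle.
- **The adverse event route.** Protocol section 7.4.1.1 says that abnormal laboratory and ECG findings "should not be reported as AEs unless they are associated with clinical signs and symptoms", lead to discontinuation, or are judged medically important by the investigator for another reason.
- **The committee's remit.** Protocol section 2.1: "A Safety Monitoring Committee (SMC) will review the safety data on a regular basis". Section 16.1 of the SMC plan describes the main aim of the meetings as monitoring the overall safety of enrolled subjects.

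**The concern.** Two rules that are reasonable separately combine badly. One limits profiles to the two most recent rounds of cohorts. The other makes profiles the only place where ECG, vital-sign and exposure values appear. Treatment continues until progression, so the subjects with the longest exposure are those whose values drop out of the package.

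The protocol's risk section (3.4.2.1) names QT/QTc prolongation as an important potential risk of M4112. A slow or delayed QTc or blood-pressure drift in longer-treated subjects at lower doses bears on whether the next higher dose is acceptable. The committee advising on that dose could be without the values. The final analysis does summarise ECGs for all treated subjects (SAP section 15.6), but only after database lock, too late to inform escalation.

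**Working it through.** The plan states no figure to reproduce. The check is a count of cohorts and a date calculation.

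**1. Cohorts without a profile.** Assume one SMC per dose level (six levels are planned, protocol 8.1). SMC k shows cohorts k and k−1, so k−2 cohorts have none, a share of (k−2)/k:

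- SMC 3: 1 of 3
- SMC 4: 2 of 4
- SMC 5: 3 of 5
- SMC 6: 4 of 6

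**2. How far the last profile reaches.** Inputs:

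- The first subject of a dose level is observed for at least 5 days before the second is dosed. In the first two cohorts the next follows at least 48 h later (SMC plan section 6). Offsets are therefore 0, 5 and 7 days.
- The SMC usually meets once the last subject finishes the 28-day DLT period (section 8). That is 7 + 28 = 35 days after the cohort's first dose.
- L is the number of days from one SMC to the next cohort's first dose. The documents do not give it; I take 0 to 90 days.
- Cycle X Day 1 is study day (X−1)×28 + 1. This gives day 29 for Cycle 2, 85 for Cycle 4, 141 for Cycle 6 and 197 for Cycle 8.

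The gap between SMCs is 35 + L. A subject's study day at the updating SMC is 1 + 35 + (35 + L) − offset. With L = 0 this is 71, 66 and 64.

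| L (days) | SMC gap (days) | Study day at last profile, subjects 1/2/3 | Latest Day 1 ECG shown |
|---|---|---|---|
| 0 | 35 | 71 / 66 / 64 | Cycle 2 |
| 14 | 49 | 85 / 80 / 78 | Cycle 4 for subject 1, Cycle 2 for the others |
| 21 | 56 | 92 / 87 / 85 | Cycle 4 for all three |
| 60 | 95 | 131 / 126 / 124 | Cycle 4 |
| 90 | 125 | 161 / 156 / 154 | Cycle 6 |

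Values falling exactly on day 85 assume that the visit took place on its planned day and was in the data at the cut-off. Slower accrual moves the limit later. For a subject who stays on treatment it does not remove it.

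**3. Whether another output fills the gap.** The listing of all treatment-emergent events, the Grade 3 or higher listing (17.1.1) and the listing of events leading to discontinuation, interruption or reduction (17.1.2) are not restricted by cohort. They carry events, not measurements. A QTc change beyond the protocol's limits requires treatment interruption (Table 1 footnote h; section 6.2.3). Interruption is not among the conditions in 7.4.1.1 that turn an ECG finding into an adverse event. An asymptomatic QTc excursion that interrupts dosing is therefore listed only if the investigator judges it medically important. A drift below those limits would ordinarily not be listed.

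**The case against.** The case against the point is substantial, and parts of it stand.

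- **The data do arrive once.** A reader might infer that later-cycle QTc and vital-sign values never reach the SMC. The documents do not support that. Every cohort's profile is updated at the following meeting, which reaches Cycle 3 even at the fastest pace. The protocol's explicit later-cycle request concerns events in the subsequent cycle, with Cycle 2 named for immune-related events (5.1, 6.2.4). The one update covers that.
- **Laboratory data.** A reader might also infer that hematology or creatinine signals in older cohorts are invisible. Section 17 says safety parameters are summarised by dose level and overall unless stated otherwise, and 17.3 grades laboratory results and analyses them on the Safety set. Sections 15, 17.4 and 17.5 do state otherwise; 17.3 does not. Its layout is vague, but cumulative laboratory summaries are not excluded.
- **Number affected.** With cohorts of 3, 4 of 6 cohorts could be read as 12 of 18 subjects. That counts everyone enrolled, including those already off treatment with no new ECGs.
- **Other routes.** A QTc change large enough to interrupt treatment may well be judged medically important and listed. After the DLT period the SMC itself defines reduced doses (6.2.3), so exposure information is not wholly lost. Safety ECGs are read locally on the day, so protection of the individual does not depend on the profiles. The SMC charter is not among the documents and may allow data requests.

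The remaining gap is in QTc and vital-sign values not recorded as adverse events, and in dosing detail unconnected with one, for subjects on treatment beyond the updated profile. The SMC plan is the document that specifies the committee's analyses, and it has no provision for these.

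**Conclusion.** The point holds in this limited form. After the SMC that follows its own review, a cohort's QTc, vital-sign and exposure values are in no planned SMC output; only abnormalities recorded as adverse events still reach the committee. The share of cohorts without profiles grows from 1 of 3 at SMC 3 to 4 of 6 at SMC 6, assuming one SMC per dose level. The number of subjects actually affected cannot be determined, because treatment durations and SMC dates are not given. The earliest ECG missed is Cycle 4 Day 1 with SMCs about 35 days apart and Cycle 6 Day 1 at about 56 days apart.

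The DLT model is untouched, since it uses all cohorts. The weakness is in the supporting safety data for dose decisions, and it is cheap to repair. Part IA has since been completed and the study terminated early (SAP sections 4 and 7), so the change matters for the plan as written and for any reuse of it.

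**What to change.** In section 16.1 of the SMC plan, replace the sentence on previous cohorts with wording such as: *Updated profiles will also be supplied for every subject of an earlier cohort in the same study part who was on treatment, or within 30 days of last dose, at any time since the previous SMC cut-off.* The last clause is needed because SMCs may be 35 days or more apart. A subject who stops just after one meeting would otherwise be past 30 days by the next and lose the final update. Thirty days matches the plan's own window for treatment-emergent events.

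As an alternative or an addition, put into 17.4 and 17.5 a cumulative listing, by dose level and for all treated subjects, of QTcF with change from baseline and of vital signs. It should run on the current cut-off, as the two adverse event listings in 17.1.1 do, because the other outputs usually use the previous one. On its own this listing would leave exposure uncovered; the profile change covers all three.

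The cost is a wording change and a longer SMC package. Even if every subject were still on treatment, it could not exceed the number enrolled (about 24 planned; protocol 8.1 allows for 24 to 30 evaluable). No new data are collected and no dosing or clinical rule changes.
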